11.1.1 Screening Visit (Visit 1, Day -35 to 0)

After signing the informed consent/assent, subjects will undergo the screening procedures to confirm eligibility to participate in the study.

The following procedures will be conducted at this visit:

- 1. Review and explain the nature of the study. Provide a visit schedule with the length of each visit to ensure that the subject can meet the requirements and has adequate transportation.
- 2. Obtain verbal and written informed consent/assent from the subject and the subject's parent or legal guardian prior to performing any study-related procedures. Provide signed copies of the consent and assent forms to the subject/parent or legal guardian.
- 3. Assign a 6-digit study number by accessing IRT which includes the 3-digit investigational center number plus a unique 3-digit subject number beginning with 001 (e.g., 101001, 101002, 101003, etc.; in this example site number is 101).
- 4. Record subject's demographic information (sex, date of birth, age, ethnicity, and race).
- 5. Record subject's medical history.
- 6. Collect a detailed history of AD, including an estimated start date, duration, and all previous medications/therapies used for AD treatment within the last 2 years.
- 7. Review all prior medications (those used within 30 days prior to the Screening Visit) and previous medications used by the subject.
- 8. Review inclusion/exclusion criteria.

- 9. Perform a urine pregnancy test³ for all females who are pre-menses (9 and older) and female subjects of childbearing potential.⁴ Exclude the subject if the pregnancy test result is positive.
 - Urine pregnancy testing is mandatory for all female subjects who are premenses (9 and older) and females of childbearing potential at Screening, Baseline, and at the Week 2, 4, 6 and 10 study visits. The decision may be made by the investigator to do additional urine pregnancy tests during the course of the study.
- 10. Obtain vital sign measurements. Vital signs will be measured after the subject is seated for at least 5 minutes, and will include systolic and diastolic blood pressure, pulse rate, respiratory rate, and oral body temperature (for younger pediatric subjects, aural or temporal temperatures will be allowed provided the same method is used for all study visits).
- 11. Measure height and weight.
- 12. Conduct an abbreviated physical examination (excluding urogenital/reproductive systems).

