11.1.2 Baseline Visit (Visit 2, Day 1)

The following procedures will be conducted at this visit:

- 1. Prior to conducting any evaluations, instruct the subject or their parent/legal guardian to complete the appropriate POEM.
- 2. Record any AEs (query subjects and their parents/legal guardians, "Are there any changes in your health since the last visit?").
- 3. Review the safety laboratory test results.

If any safety laboratory test results obtained at the Screening Visit, which will be received by the investigator prior to conducting the Baseline Visit, are abnormal and clinically significant as determined by the investigator, the investigator should discuss with the medical monitor whether it is in the subject's best interest to participate in the study prior to enrolling.

- 4. Confirm the subject's medical history and prior medication uses.
- 5. Review all concomitant medications or therapies and new medications / therapies started since the last study visit, including use of bland emollients.
- 6. Perform a urine pregnancy test for all female subjects who are pre-menses (9 and older) and females of childbearing potential. Exclude the subject if the pregnancy test result is positive.
- 7. Perform an evaluation of the subject's TBSA affected by AD.
- 8. Perform an IGA.
- 9. Perform EASI evaluations.
- 10. Perform an evaluation of the other signs and symptoms of AD (hyper/hypopigmentation, dry skin).
- 11. Assess pruritus and sleep disturbance.
- 12. Instruct the subject or their parent/legal guardian to assess the degree to which the subject's AD was controlled in the 7 days immediately prior to the visit (i.e., the subject's assessment of AD).
- 13. Review inclusion/exclusion criteria. If the subject continues to meet all inclusion criteria and none of the exclusion criteria, randomize the subject by accessing the interactive response technology (IRT) system.
- 14. At select sites only obtain standardized representative photos (refer to the study-specific photography manual for further details). Photos taken will include a target lesion and full front/back images (please refer to photography manual for details).

- 15. Obtain the IRT-assigned study drug kit (containing two tubes), remove and weigh the tubes (individually) to be dispensed to the nearest tenth of a gram, and complete the study drug accountability record. Dispense both tubes to the subject and/or their parent/legal guardian and review the dosing instructions.

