- 16. Instruct the subject and their parent/legal guardian on diary completion and dispense diary. The subject, or parent/legal guardian as necessary, will record daily study drug applications and if applicable, bland emollient applications.
- 17. The subject or their parent/legal guardian will apply the first dose of study drug in the investigational center. Instruct the subject and their parent/legal guardian in the proper application technique for the study drug and provide the appropriate Subject Instruction Sheet with dosing instructions (Appendix 17.1).
- 18. Record any AEs following the initial treatment application.
- 19. Remind the subject, or parent/legal guardian, to refrain from applying the study drug and non-medicated topical products (e.g., sunscreens, lotions, creams, bland emollients) the morning of the next study visit.
- 20. Schedule the next study visit (Visit 3 [Week 1]) in 7 days (\pm 2 days).

11.1.3 Visit 3 (Week 1 [± 2 days]), Visit 4 (Week 2 [± 2 days]), Visit 5 (Week 4 [± 3 days]), and Visit 6/Early Termination (ET) Visit (Week 6 [-3/+5 days])

Visits are to be scheduled in reference to Visit 2 (Baseline). The following procedures will be conducted at these visits:

- 1. Record any AEs (query subjects and their parents/legal guardians, "Are there any changes in your health since the last visit?").
- 2. Review concomitant medications.
- 3. With the exception of Week 1 (Visit 3), conduct a urine pregnancy test on all premenses females (9 and older) and female subjects of childbearing potential (discontinue any subject from the study who has a positive test result).
- 4. Perform an evaluation of the subject's TBSA affected by AD.
- 5. Perform an IGA.
- 6. Perform EASI evaluations.
- 7. Perform an evaluation of the other signs and symptoms of AD (hyper/hypopigmentation, dry skin).
- 8. Assess pruritus and sleep disturbance.
- 9. Instruct the subject or their parent/legal guardian to assess the degree to which the subject's AD was controlled in the 7 days immediately prior to the visit (i.e., the subject's or parent's/legal guardian's assessment of AD).

- 10. At Visits 4, 5, and 6 (Weeks 2, 4, and 6) only: Collect used/unused study drug tubes and completed diary from the subject or parent/legal guardian. At Visits 3-6 (Weeks 1, 2, 4 and 6), review the diary for treatment compliance with the subject/parent/legal guardian.

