11.3.4 Adverse Events

An AE is any untoward medical occurrence in a subject or clinical investigation subject administered a medicinal product and which does not necessarily have a causal relationship with the study drug. Thus, AEs include any unfavorable and unintended illness, sign, symptom, clinically significant laboratory test abnormality, or disease temporally associated with the use of a medicinal product that has appeared or worsened during the course of the clinical study, regardless of causal relationship to the study drug(s) under study. The collection of non-serious AEs and serious AEs (SAEs) should begin following the subject's completion of the consent/assent process to participate in the study.

Descriptions of AEs will include the dates of onset and resolution, maximum severity, seriousness, action taken regarding study drug, corrective treatment, outcome, and investigator's assessment of causality. Worsening of disease will not be considered an AE unless it results in discontinuation of the subject from the study or requires medical intervention prohibited by the protocol. All AEs will be followed to resolution or until stable as determined by the investigator.

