11.3.4.2 Assessment of Severity and Causality of Adverse Events

The severity assigned to an AE should be determined by the maximum severity of the AE. The categories described below should be used to estimate the severity of AEs:

- Mild: Awareness of a sign or symptom but is easily tolerated, requires no treatment and does not interfere with subject's daily activities.
- Moderate: Low level of concern to the subject and may interfere with daily activities, but can be relieved by simple therapeutic care.
- Severe: Interrupts the subject's daily activity and requires systemic therapy or other treatment.

The investigator should assess the relationship of the AE, if any, to the study drug as either "Related" or "Not Related."

- **Related:** There is at least a reasonable possibility that the AE/SAE is related to the study drug. Reasonable possibility means that there is evidence to suggest a causal relationship between the drug and the AE.
- **Not Related:** There is little or no reasonable possibility that the AE/SAE is related to the study drug. This assessment implies that the AE/SAE has little or no temporal relationship to the study drug and/or a more likely or certain alternative etiology exists.

The following should be taken into account when assessing AE/SAE causality:

- Positive temporal relationship to study drug, such as if the study drug was withdrawn and the SAE resolved or the event recurred after re introduction
- If there is a reasonable possibility that the AE is associated with an underlying or concomitant illness
- Possible association with previous or concomitant therapy

- No temporal relationship to the study drug and/or a more likely alternative etiology exists
- If the AE is directly related to study procedures or there is a lack of efficacy

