11.3.4.3 Procedures for Reporting Adverse Events and Serious Adverse Events

Throughout the course of the study, efforts will be made by the investigator to remain alert to possible AEs that are either systemic or ocular in nature. The period of observation for collection of AEs extends from the time the subject and parent/legal guardian gives informed consent/assent until the last study visit or discontinuation from the study. The first concern will be the safety of the subject, and appropriate medical intervention will be made.

The investigator or designee will elicit reports (i.e., via direct questioning, observation, clinical evaluation) of AEs from the subject at each study visit and record all AEs. The investigator will document the dates of onset, progress, outcome, and resolution of such AEs. The investigator will also provide an assessment of all AEs as to the severity, causal relationship to study drug, and causal relationship to study protocol.

It is the investigator's responsibility to document all AEs that occur during the study. The AEs should be documented as a single medical diagnosis. When this is not possible, the AE should be documented in terms of signs and/or symptoms observed by the investigator or reported by the subject and/or their parent/legal guardian at each study visit.

All AEs occurring after the subject and their parent/legal guardian signs the assent/informed consent through the last study visit must be reported, regardless of whether or not the AEs are considered drug-related. All AEs, whether in response to a query, observed by the clinical center personnel, or reported spontaneously by the subject and/or their parent/legal guardian, will be recorded.

At each visit during the study, the subject will be assessed for the occurrence of new and ongoing AEs. Cutaneous tolerability signs and symptoms that result in the subject's requiring a concomitant therapy or discontinuation from the study will be reported as an AE. The following data will be collected on all AEs and recorded on the appropriate eCRF:

- Event name (diagnosis preferred, if unknown, record the signs/symptoms)
- Onset date and end date
- Maximum intensity (severity)
- Seriousness
- Action taken regarding study drug

- Corrective treatment, if given
- Outcome

In addition, the investigator's assessment of causality will be recorded.

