12.6 Safety

12.6.1 Adverse Events

The primary analysis of safety will be conducted at Week 6. There will be a separate tabulation of the AEs that start in the period post Week 6, to Week 10 visit. All AEs occurring during the study will be recorded and classified using terminology from the Medical Dictionary for Regulatory Activities (MedDRA). All reported treatment-emergent adverse events (TEAEs), defined as any AE with an onset on or after the date of first study drug application, will be summarized by treatment group and will provide the number of subjects reporting TEAEs, system organ class, preferred term, severity, and relationship to study drug. When summarizing TEAEs by severity or relationship to study drug, each subject will be counted only once within a system organ class or a preferred term using the event with the greatest severity or causality, respectively, within each category. All reported SAEs will be summarized by the number of subjects reporting the event, system organ class, preferred term, severity, and relationship to study drug.

All information pertaining to AEs noted during the study will be listed by treatment group and subject and will include a verbatim description of the event as reported by the investigator, as well as the preferred term, system organ class, start date, stop date (if stopped), seriousness, severity, action taken regarding the study drug, corrective treatment, outcome, and relationship to the study drug. In addition, a listing of subjects who prematurely discontinue from the study due to AEs will be provided as well as a listing of subjects who reported an SAE.

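### Treatment-emergent status rests on onset date alone, so a non-serious adverse event that starts in screening and worsens on study drug can drop out of the TEAE tables

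*Combined protocol and SAP*

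**What the plan says.** - **TEAE rule.** Section 12.6.1 defines a treatment-emergent AE as "defined as any AE with an onset on or after the date of first study drug application". The TEAE tables report subjects by system organ class, preferred term, severity and relationship to study drug.
- **Other AE outputs.** The same section summarizes every reported SAE, whether or not it is treatment-emergent. It lists all AEs with start date, stop date, severity, action taken and relationship, and separately lists subjects who discontinue because of AEs.
- **Start of collection.** Section 11.3.4 states: "The collection of non-serious AEs and serious AEs (SAEs) should begin following the subject's completion of the consent/assent process". Section 11.1.1 and Table 1 place screening between Day -35 and Day 0.
- **What an AE is.** Section 11.3.4 covers a condition "that has appeared or worsened during the course of the clinical study".
- **How an AE is recorded.** Section 11.3.4.2 says: "The severity assigned to an AE should be determined by the maximum severity of the AE". The field list in section 11.3.4.3 gives "Onset date and end date" and one maximum intensity. It has no field for the date of a change in severity.
- **Baseline Visit.** Section 11.1.2 has two AE steps. Item 2, before dosing, asks "Are there any changes in your health since the last visit". Item 18, after dosing, reads "Record any AEs following the initial treatment application".
- **SAP.** Sections 12 and 12.8 refer to a separate SAP. The supplied text contains no wider TEAE definition.

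**The concern.** The protocol gathers AEs for up to five weeks before any study drug is applied and accepts worsening as an AE concept. It then leaves worsening out of the rule that decides which events enter its main safety tables. An AE that is mild in screening and becomes severe on treatment would have a pre-dose onset date and so fail the rule, even if the investigator judged it related to study drug.

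What could be lost is between-arm information. Randomization should make the arms comparable, apart from chance, in the events that subjects bring to Day 1. A difference in how often those events worsen afterwards is what the vehicle comparison could reveal. Respiratory infection or headache already present at first dose are plausible examples. Worsening of atopic dermatitis itself falls under a separate rule in section 11.3.4 and is not the subject of this point.

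**Working it through.** No sample size, power or alpha figure is involved, and the plan states no figure that could be reproduced here. The check applies the written rule to defined cases and then reads the recording sections beside it.

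**Inputs**
- First application is on Day 1 (sections 9.1 and 11.1.2).
- Screening runs from Day -35 to Day 0 (section 11.1.1), which is 0 - (-35) + 1 = 36 calendar days counting both ends.
- Onset is held as a date (section 11.3.4.3).

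**Rules compared**
- Written rule (12.6.1): TEAE if onset day ≥ 1.
- Amended rule: TEAE if onset is later than Day 1, or on Day 1 after the first application, or before the first application with worsening after it.

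| Case | Written rule | Amended rule |
|---|---|---|
| (a) Onset Day -20, worsens Day 10, kept as one record | -20 ≥ 1 is false: not TEAE | TEAE |
| (b) Onset Day -20, unchanged, found at Baseline | -20 ≥ 1 is false: not TEAE | not TEAE |
| (c) Onset Day 1, before first application | 1 ≥ 1 is true: TEAE | not TEAE |
| (d) Onset Day 1, after first application | 1 ≥ 1 is true: TEAE | TEAE |
| (e) Onset Day 10 | 10 ≥ 1 is true: TEAE | TEAE |

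Only (a) and (c) change.

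**Is case (a) what the recording rules produce?** Section 11.3.4.2 gives an AE the worst severity it reaches. Section 11.3.4.3 gives it one onset date and one end date. Read together, they point to a single record for the Day -20 event, with a pre-dose onset and the severity reached on Day 10. Nothing tells the site to close that record and open another. The event then misses every TEAE table, including those by severity and relationship.

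**Can the listing repair it?** Only in part. It shows a start date, a stop date and one severity. A reader cannot tell whether a screening-onset event reached its worst severity before or after the first application.

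**Is case (c) real?** Yes, but it is narrow. The two steps in section 11.1.2 mean the site can know on which side of the first application a Day 1 event began. The date-only field does not keep that information.

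**The case against.** The strongest objection is that the documents do not require case (a) to be excluded. Section 11.3.4 speaks of conditions that appeared or worsened, so a site could treat the worsening as an AE in its own right, with onset on the day it worsened. The written rule would then count it. This stands as a limit: exclusion follows from the likeliest reading of the recording sections and is not stated. It does not remove the problem, because classification would then depend on each site's habit.

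The other safeguards are real. Serious worsening stays tabulated, all AEs are listed, discontinuations due to AEs are listed, and section 12.6.2 gives laboratory shifts from Screening to Week 6. The gap is therefore confined to non-serious worsening, which has no between-arm summary as an AE.

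Some stronger readings are tempting but unsupported:
- **That any event found at Baseline before dosing becomes treatment-emergent.** The rule uses onset, not detection. The pre-dose question looks back to the previous visit, so most events it finds will have begun before Day 1 and are correctly excluded, as in case (b). Only an onset on Day 1 itself is affected. That error over-counts and, arising before any drug is applied, should not favour either arm.
- **That a worsened screening event can never count.** A new record opened at the worsening would count.
- **That the length of screening measures the problem.** The window says nothing about how many AEs are ongoing at first dose, and fewer still would worsen.
- **That screening-onset skin infection is the main worry.** Exclusions 2 and 6, rechecked at Baseline before randomization, would remove most such subjects.

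A separate SAP might also contain a wider definition. That cannot be checked from the supplied text.

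**Conclusion.** The concern holds in limited form. The written rule misclassifies two kinds of event. The one that matters is a non-serious AE that starts in screening, worsens after the first application and remains one record: it is absent from the TEAE tables and visible only in listings that do not date the worsening. The minor one is a Day 1 onset before the first application, which is counted as treatment-emergent.

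The number of subjects affected cannot be estimated. The documents give no rate of screening AEs, of AEs ongoing at first dose, or of their worsening. The conclusion assumes that sites follow the recording sections on their plain reading and that no SAP text widens the definition. The change is worth making because the error lies in a stated rule and is cheap to correct. Nothing here shows that a safety signal has been or will be missed.

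**What to change.** 1. In section 12.6.1 and the SAP, define a TEAE as any AE that starts after the first application, or that starts before it and worsens in severity or becomes serious after it.
2. In section 11.3.4.3 and the eCRF guidance, instruct sites to record such worsening as a new AE dated at the worsening. State in section 11.3.4.2 that the original record keeps the maximum severity reached up to that point. This step matters most: if the date of worsening is not collected, later programming cannot recover it.
3. Add a flag for Day 1 onsets showing whether the event began before or after the first application, completed from the two AE steps already made at Baseline. State in the SAP how an unanswered flag is handled.

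The cost is a few sentences, one eCRF instruction and one flag. This is a small amount of new data collection. TEAE counts would differ slightly: some worsened screening events would enter and some pre-dose Day 1 events would leave. Section 12.6.1 already counts a subject once per preferred term when summarizing by severity or relationship, so the extra record would not double-count the subject in those tables.

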12.6.2 Clinical Laboratory Tests

Changes from Baseline in safety laboratory values (hematology, serum chemistry, and urinalysis) will be summarized with descriptive statistics for each treatment group at all applicable study visits.

Shift tables will be presented for changes in safety laboratory values to summarize laboratory test results collected at Screening and Week 6. Normal ranges established by the central laboratory will be used to determine the shifts. A listing of all out-of-range laboratory test results at any assessment time point will also be provided. Determination of clinical significance for all out-of-range laboratory values will be made by each investigator and included in the listing. In addition, a listing of all clinically significant laboratory test results will be provided.

